6.6 Dose delay and dose modification

6.6.1 Dose delay

Treatment with acalabrutinib should be held for any unmanageable, potentially study drug-related toxicity that is Grade ≥ 3 in severity. Any other clinically important events where dose delays may be considered appropriate by the investigator must be discussed with the sponsor. Study drug may be held for a maximum of 28 consecutive days from expected dose. Study treatment should be discontinued in the event of a toxicity requiring the postponement of dosing lasting >28 days, unless reviewed and approved by the sponsor.

Note: temporary withholding of study drug for as little as 7 days can cause a transient worsening of disease and/or of constitutional symptoms. Refer to Section 7.1 for more information on assessing disease progression under these circumstances.

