6.6.2 Dose modification

The actions in Table 7 should be taken for the following toxicities (according to CTCAE criteria version 5.0 or higher):

- Grade 4 neutropenia (ANC $< 500/\mu\text{L}$) for > 7 days (Myeloid growth factors are permitted per Consensus of Chinese Experts ([Version 2015](#)) and use must be recorded on the eCRF).

- Grade 3 platelets decreases in the presence of clinically significant bleeding
- Grade 4 platelets decreases
- Grade 3 or 4 nausea, vomiting, or diarrhea, if persistent despite optimal antiemetic and/or anti-diarrheal therapy
- Any other Grade 4 toxicity or unmanageable Grade 3 toxicity.

If the toxicity resolves or reverts to \leq CTCAE grade 1 or baseline within 28 days of onset and the subject is showing clinical benefit, treatment with acalabrutinib may be restarted using the rules below for dose modifications (see [Table 7](#)). Whenever possible, any dose adjustment of acalabrutinib should be discussed between the investigator and the sponsor before implementation. The appropriate clinic staff should dispense the study drug for the new dose level and instruct the subject/caregiver about the change in dose level. Any changes to the dosing regimen must be recorded in the appropriate eCRF.

In case a dose reduction is necessary, the study intervention will be administered as follows.

Dose modification guidelines for study intervention-related toxicities are provided below. Appropriate and optimal treatment of the toxicity is assumed prior to considering dose modifications. Prior to discontinuation of study intervention due to toxicities, please consult with the study physician.

Table 7 Dose modifications for toxicity

Occurrence	Action
1 st -2 nd	Hold acalabrutinib until recovery to Grade \leq 1 or baseline; may restart at original one-day dose level (100 mg BID)
3 rd	For non-hematologic AEs, discontinue acalabrutinib. For thrombocytopenia with significant bleeding, discontinue acalabrutinib. For other hematologic AEs, upon recovery to Grade \leq 1 or baseline, restart at 100 mg QD.
4 th	For hematologic AEs, discontinue acalabrutinib.

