2.2. Protocol deviations

For this study, the following general categories will be considered important protocol deviations (IPDs) and most of them (programmable IPDs) will be programmatically derived from the electronic case report form (eCRF) data. Few observable IPDs may only be identified by site monitoring activities as the data is not captured in any clinical data base.

- Inclusion criteria deviations
- Exclusion Criteria Deviations
- Discontinuation Criteria for study product met but participant not withdrawn from study treatment

- Discontinuation Criteria for overall study withdrawal met but patient not withdrawn from study
- Investigational Product (IP) deviation
- Excluded medications taken
- Deviations to study procedure
- Other Important Deviations

IPD categories are defined and managed by the study team during the IPD reviews throughout the study before database lock. These definitions of IPD categories, sub-category codes, and descriptions will be used during the course of the study. The final IPD list is used to produce the Summary of IPDs output and the Listing of Subjects with IPDs. No deviations will lead to patients being excluded from the analysis sets described in Section 2.1 (with the exception of the pharmacokinetics analysis set, if the deviation is considered to impact upon PK).

A per-protocol efficacy analysis excluding patients with significant protocol deviations is not planned. However, a 'deviation bias' sensitivity analysis may be performed on the ORR endpoint excluding patients with deviations that may affect the efficacy of the trial therapy if >10% of patients in either cohort of Phase 2 portion: Did not have the intended disease or indication.

The need for such a sensitivity analysis will be determined following review of the protocol deviations ahead of database lock and will be documented prior to the primary analysis being conducted.

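### Protocol Sections 6.6.1 and 6.6.2 start the 28-day limit from different dates and use different hold triggers, so the same toxicity can be handled differently under each

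*Protocol*

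**What the plan says.** **Section 6.6.1 (Dose delay).** The trigger is: "Treatment with acalabrutinib should be held for any unmanageable, potentially study drug-related toxicity that is Grade ≥ 3 in severity". Other clinically important events for which the investigator considers a delay appropriate must be discussed with the sponsor. The limit is: "Study drug may be held for a maximum of 28 consecutive days from expected dose". A toxicity that postpones dosing for longer than this leads to discontinuation, except where the sponsor has looked at the case and agreed to continue.

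**Section 6.6.2 (Dose modification).** Table 7 applies to a separate list:
- Grade 4 neutropenia lasting more than 7 days
- Grade 3 platelet decreases accompanied by significant bleeding
- Grade 4 platelet decreases
- Grade 3 or 4 gastrointestinal toxicity that persists under optimal treatment
- "Any other Grade 4 toxicity or unmanageable Grade 3 toxicity"

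Restart is permitted when the toxicity has come down to Grade 1 or lower, or to "baseline within 28 days of onset and the subject is showing clinical benefit". No sponsor exception is stated.

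**Table 7.** For the first and second occurrence, drug is held until recovery, with no time limit in the row. The third and fourth occurrences lead to a lower dose or to discontinuation, depending on the type of event.

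**Section 7.1.** The list of reasons for stopping treatment has a general adverse-event criterion and no 28-day item.

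None of these places says which of 6.6.1 and 6.6.2 prevails.

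**The concern.** Both sections use the figure 28, so they look like one rule. They measure different things. Section 6.6.1 measures the length of the interruption. Section 6.6.2 measures the time from onset of the toxicity to its recovery. The two agree only when drug is withheld from the day of onset. For neutropenia, the duration condition in 6.6.2 pushes the hold past onset by design.

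At stake are whether a subject is held, whether the subject may restart, and whether the event counts as a Table 7 occurrence. Cytopenia is a named identified risk in Section 2.3.2.2, so these are not remote cases. The decisions feed the SAP summaries of dose withholding (SAP 3.2.2.2 and 4.2.3.2) and of TEAEs leading to discontinuation or interruption (SAP 4.2.3.3.3 and 4.2.3.3.4).

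Protocol Section 8.3.7 adds a further link. Worsening of a protocol-mandated laboratory value is reported as an adverse event only if it is serious or is the reason for stopping drug, unless associated signs or symptoms are reported. For a silent, non-serious cytopenia, the choice of limit could therefore decide whether an adverse event is recorded at all.

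**Working it through.** **Clock.** The plan gives no figure to reproduce, so this is a day count. Let onset be day 0, g the day of the first withheld dose, and r the day of recovery. Assume that dosing would resume on day r.

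- Section 6.6.1, without sponsor approval: r − g ≤ 28, so r ≤ 28 + g.
- Section 6.6.2: r ≤ 28.
- Conflict, for g from 1 to 28: 28 < r ≤ 28 + g, which is g days.

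| Hold starts on day g | Latest recovery under 6.6.1 | Latest recovery under 6.6.2 | Days in conflict |
|---|---|---|---|
| 0 | 28 | 28 | none |
| 1 | 29 | 28 | 29 (1 day) |
| 3 | 31 | 28 | 29–31 (3 days) |
| 7 | 35 | 28 | 29–35 (7 days) |
| 8 | 36 | 28 | 29–36 (8 days) |
| 14 | 42 | 28 | 29–42 (14 days) |

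The reverse conflict never occurs when the hold starts on or after onset, because r ≤ 28 implies r − g ≤ 28.

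Worked case: Grade 4 neutropenia starts on day 0, the more-than-7-days condition is met and drug is held on day 8, and the count recovers on day 32. The hold is 32 − 8 = 24 days, within 6.6.1. Recovery is 32 days after onset, outside 6.6.2.

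**Sponsor exception.** Suppose both conditions must be met. A toxicity that keeps drug withheld for more than 28 days, from a hold starting on or after onset, recovers more than 28 days after onset. Section 6.6.2 then offers no restart, so the exception in 6.6.1 has almost no effect.

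**Triggers.**

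| Event | 6.6.1 | 6.6.2 |
|---|---|---|
| Grade 4 platelet decrease, judged manageable | No directed hold; sponsor discussion | Table 7 action |
| Other Grade 4 toxicity, judged manageable | No directed hold; sponsor discussion | Table 7 action |
| Grade 4 neutropenia of 7 days or less, unmanageable and possibly related | Directed hold | Neutropenia item not met |

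The trigger differences decide whether drug is held and whether an occurrence is counted. They do not cause the restart conflict, which comes from the clock.

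**The case against.** The best defence is that the sections can be read together. Section 6.6.1 caps the hold and says when to discontinue; it grants no restart. Section 6.6.2 is permissive and does not expressly order discontinuation after day 28. Recovery within 28 days of onset always satisfies the 6.6.1 cap if the hold starts on or after onset. Section 6.6.2 also asks for sponsor discussion of dose adjustments where possible and for study-physician consultation before discontinuation for toxicity. The synopsis, Section 4.1 and the cytopenia text in 2.3.2.2 all point to 6.6.2. This makes an unnoticed split between sites less likely. It does not remove the mismatch: the combined reading empties the sponsor exception, and nothing in the text says that it is the intended reading.

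Several stronger readings are tempting but not supported:
- **That 6.6.1 allows holds only for unmanageable toxicity.** It does not say so; other events may be delayed after sponsor discussion. The word unmanageable is also undefined.
- **That 6.6.2 ignores causality.** Its trigger list is silent, but the text introducing Table 7 limits the guidance to toxicities related to study drug, and Section 6.7 describes it in the same way.
- **That these are the only stopping rules for cytopenia.** Section 7.1 has a general adverse-event criterion.
- **That the SAP deviation category "Discontinuation Criteria for study product met but participant not withdrawn from study treatment" is directly affected.** Protocol Section 6.1.2 places the discontinuation criteria in Section 7.1, which has no 28-day item, so the link is not shown.
- **That relative dose intensity becomes undefined.** It uses the doses actually taken and can be calculated under either reading.
- **That onset cannot be dated in Cohort B because later visits are 12 weeks apart.** Adverse-event start dates are collected, and extra samples are allowed when clinically indicated.

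**Conclusion.** The inconsistency is real and worth correcting. The different clock starts, and the exception stated in only one section, are plain from the text. The trigger mismatch is also textual, although its practical reach depends on how sites interpret manageability.

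The conflict lasts g days for a hold that starts g days after onset, for g up to 28. It is zero when the hold starts on the day of onset, and 8 days for Grade 4 neutropenia held from day 8. That last figure assumes onset is counted as day 0, the hold starts when the 6.6.2 trigger is met, and dosing resumes on recovery. The proper statement is that the same toxicity can be treated differently, not that it always is.

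The documents give no basis for estimating how many subjects would be affected, and the number may be small. A reader might take one subject in 60 (1/60 = 1.7 percentage points in Cohort B) as the effect size, but that is only the weight of one subject, not a frequency. The BICR-assessed ORR analysis and the sample sizes of 33 and 60 are untouched.

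**What to change.** Reconcile Sections 6.6.1, 6.6.2 and Table 7 so that they share:

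1. one trigger list, stating for each item whether manageability and relatedness are required and how the duration condition for neutropenia fits with the general hold rule;
2. one start date for the 28-day limit;
3. one statement of whether the sponsor exception applies, and what follows when the limit passes without it.

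Then cross-refer Section 7.1, and any deviation check for subjects who should have stopped drug, to that single rule. Which trigger, start date and exception to adopt is a clinical decision for the sponsor's physicians; this point asks only that the passages agree.

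The cost is a short protocol amendment and, where a deviation check uses the rule, an update to its specification. No additional data are needed.

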6.6.2 Dose modification

The actions in Table 7 should be taken for the following toxicities (according to CTCAE criteria version 5.0 or higher):

- Grade 4 neutropenia (ANC $< 500/\mu\text{L}$) for > 7 days (Myeloid growth factors are permitted per Consensus of Chinese Experts ([Version 2015](#)) and use must be recorded on the eCRF).

- Grade 3 platelets decreases in the presence of clinically significant bleeding
- Grade 4 platelets decreases
- Grade 3 or 4 nausea, vomiting, or diarrhea, if persistent despite optimal antiemetic and/or anti-diarrheal therapy
- Any other Grade 4 toxicity or unmanageable Grade 3 toxicity.

If the toxicity resolves or reverts to \leq CTCAE grade 1 or baseline within 28 days of onset and the subject is showing clinical benefit, treatment with acalabrutinib may be restarted using the rules below for dose modifications (see [Table 7](#)). Whenever possible, any dose adjustment of acalabrutinib should be discussed between the investigator and the sponsor before implementation. The appropriate clinic staff should dispense the study drug for the new dose level and instruct the subject/caregiver about the change in dose level. Any changes to the dosing regimen must be recorded in the appropriate eCRF.

In case a dose reduction is necessary, the study intervention will be administered as follows.

Dose modification guidelines for study intervention-related toxicities are provided below. Appropriate and optimal treatment of the toxicity is assumed prior to considering dose modifications. Prior to discontinuation of study intervention due to toxicities, please consult with the study physician.

Table 7 Dose modifications for toxicity

Occurrence	Action
1 st -2 nd	Hold acalabrutinib until recovery to Grade \leq 1 or baseline; may restart at original one-day dose level (100 mg BID)
3 rd	For non-hematologic AEs, discontinue acalabrutinib. For thrombocytopenia with significant bleeding, discontinue acalabrutinib. For other hematologic AEs, upon recovery to Grade \leq 1 or baseline, restart at 100 mg QD.
4 th	For hematologic AEs, discontinue acalabrutinib.

6.7 Treatment after the end of the study

Any subjects still receiving investigational product at the time of the 2nd data cut-off of phase I and cohort A and the 3rd data cut-off of cohort B will be able to continue to receive acalabrutinib while deriving clinical benefit in the opinion of the Investigator, and not meet the discontinuation criteria. Administration of investigational product following final data cut-off will be recorded in site documents for supply management but will not be collected on the eCRF. It is recommended that investigators monitor the participant's safety laboratory results periodically during treatment with acalabrutinib in order to manage AEs, consistent with the dose modification guidelines for management of study intervention-related toxicities (see

Section 6.6). Such subjects will continue to be monitored for all AE up to 30 days after the last dose of investigational product.

In the event that a roll-over or safety extension study is available at the time of the study closure, subjects who are still on treatment at the end of the study and deriving clinical benefit from acalabrutinib treatment may be eligible to enroll in a separate rollover study. The roll-over or safety extension study would ensure treatment continuation with visit assessments per its protocol.

7. DISCONTINUATION OF TREATMENT AND SUBJECT WITHDRAWAL

7.1 Discontinuation of study treatment

Subjects may be discontinued from investigational product in the following situations. Note that discontinuation from study treatment is NOT the same thing as a complete withdrawal from the study.

- Any subject who has objective evidence of disease progression while receiving protocol required study drug should be withdrawn from the study treatment. If there is uncertainty regarding whether there is disease progression, the subject may continue study treatment and remain under disease evaluation until confirmation of disease progression. In particular, transient worsening of disease during temporary interruption of study therapy (e.g., for drug-related toxicity, surgery, or intercurrent illness) may not indicate disease progression. In such circumstances, and if medically appropriate, subjects may resume therapy and relevant clinical, laboratory, and/or radiographic assessments should be done to document whether Tumor control can be maintained or whether actual disease progression has occurred.
- Any adverse event presents a substantial clinical risk to the subject with continued acalabrutinib dosing.
- Subject decision. The subject is at any time free to discontinue treatment, without prejudice to further treatment.
- Pregnancy in a subject, intend to become pregnant or begin breast feeding.
- Severe non-compliance with the Clinical Study Protocol.
- Start of alternative anticancer therapy.
- Study terminated by Sponsor.

See the SoA (Section 1.1) for data to be collected at the time of treatment discontinuation and follow-up and for any further evaluations that need to be completed.

7.1.1 Procedures for discontinuation of study treatment

The investigator should instruct the subject to contact the site before or at the time if study treatment is stopped. A subject that decides to discontinue study treatment will always be

asked about the reason(s) and the presence of any AEs. The date of last intake of study treatment should be documented in the eCRF. All study treatment should be returned by the subject at their next on-site study visit or unscheduled visit. Subjects permanently discontinuing study treatment should be given locally available standard of care therapy, at the discretion of the Investigator.

Discontinuation of study treatment, for any reason, does not impact on the subject's participation in the study. The subject should continue attending subsequent study visits and data collection should continue according to the study protocol.

The end of treatment visit should be performed within 7 days of the last dose of study drugs, if possible, and is not required for subjects who discontinue from study treatment within 10 days of a scheduled study visit or if the EoT visit would be performed within 14 days of the Safety Follow-up visit. 30 day (+ 7 days) safety follow-up visit is required for all subjects after his or her last dose of study drug to monitor for AEs, regardless of whether the subject receives a new anticancer therapy or demonstrates disease progression within this timeframe.

If the subject does not agree to continue in-person study visits, a modified follow-up must be arranged to ensure the collection of endpoints and safety information. This could be a telephone contact with the subject at end of treatment follow up visit, a contact with a relative or treating physician, or information from medical records. The approach taken should be recorded in the medical records. A subject that agrees to modified follow-up is not considered to have withdrawn consent or to have withdrawn from the study.

7.1.2 Follow-up for progression and survival

Post-treatment Disease Follow up: All R/R MCL subjects enrolled in Phase 1 portion or subjects in Phase 2 portion and all R/R CLL subjects enrolled in Phase 2 portion who discontinue from study treatment due to reasons other than disease progression will be followed for disease evaluation approximately every 12 weeks or 24 weeks (\pm 7 days) from the latest date of disease evaluation before study treatment discontinuation until disease progression, regardless of whether the subject receives a new anticancer therapy. During this period, CT scans will be done approximately 12 weeks or 24 weeks.

Survival Follow up: R/R MCL subjects in Phase 1 or subjects in Phase 2 and R/R CLL subjects in Phase 2 who have disease progression, and have not withdrawn consent will be contacted approximately every 12 weeks by clinical visit or telephone, to assess survival and the use of alternative anticancer therapy until death or lost to follow up. At the time of the planned final analysis, a survival sweep may be conducted. All subjects who are on study and not known to have died before the survival sweep may be contacted at that time.

7.2 Lost to follow-up

A subject will be considered potentially lost to follow-up if he or she fails to return for scheduled visits and is unable to be contacted by the study site.

The following actions must be taken if a subject fails to return to the clinic for a required study visit:

- The site must attempt to contact the subject and reschedule the missed visit as soon as possible and counsel the subject on the importance of maintaining the assigned visit schedule.
- Before a subject is deemed lost to follow up, the investigator or designee must make every effort to regain contact with the subject or through their family, or by contact with subject's current physician by e.g. repeat telephone calls, certified letter to the subject's last known mailing address or local equivalent methods. If publicly death registry is available, death information (i.e. Date of death) should be collected where allowed by Regulatory and EC Requirements.
- All attempts to contact the subject should be made routinely and recorded in eCRF on the survival status module. The site should report the attempted date of contact and the last date known to be alive.
- If contact or registry/public source was unsuccessful (or no clear status could be obtained) choose subject status "unknown" and continue the contact attempts until end of the study (until final analysis).
- Patients should not be marked as lost to follow-up on the Termination (DS) module until the end of the study (at final analysis) when all attempts to collect survival follow-up have been exhausted.
- At the time of final analyses, all enrolled subjects' survival status in the safety analysis set should be re-checked, this includes those subjects who withdraw consent or are classified as "lost to follow up."
 - Lost to Follow up - site personnel should check hospital records, the subjects' current physician, and a publicly available death registry (if available) to obtain a current survival status in the 7 days following data cut-off. (The SURVIVE module will be updated.)
 - In the event that the subject has actively withdrawn consent to the processing of their personal data, the survival status of the subject can be obtained by site personnel from publicly available death registries (if available) where it is possible to do so under applicable local laws to obtain a current survival status in the 7 days following data cut-off. (The applicable CRF modules will be updated.)

